5.7. Analyses of Efficacy Variables

The analysis of efficacy data will be performed based on the FAS, as defined in Section 3.1.

5.7.1. Analysis of Primary Efficacy Variable

Primary efficacy analysis will be performed when the last patient enrolled has had the opportunity for at least 4 tumor assessments.

The ORR according to investigator review will be summarized and the corresponding 2-sided 95% confidence interval will be derived using a normal approximation of the binomial distribution.

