chemotherapy arm had a median survival of 8.5 months (95% CI 7.5 months to 9.6 months). In addition to a survival benefit, patients had a clinically and statistically significant improvement in progression free survival (PFS) and overall response rate (ORR) (Tewari, 2021). Patients on the cemiplimab arm had an ORR of 16.4% (95% CI 12.5% to 21.1%). Patients on the chemotherapy arm had an ORR of 6.3% (95% CI 3.8 to 9.6%) (Press Release: Phase 3 Trial of Libtayo® (cemiplimab) Monotherapy in Advanced Cervical Cancer Stopped Early for Positive Result on Overall Survival, 2021).

[figure not shown]
Additional information, including preclinical and clinical safety data, is available in the Investigator's Brochure.

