11.1. Statistical Hypothesis

This is a single arm, open label study and there is no formal statistical hypothesis in this study.

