11.2. Justification of Sample Size

The planned total sample size for this study is 105 patients.

The primary objective of the study is to estimate the clinical benefit of cemiplimab + ISA101b after progression on first line chemotherapy, as assessed by objective response rate (ORR). With 105 patients, Table 3 below presents various response rates and associated 2-sided 95% CIs using a normal approximation of the binomial distribution, and precision of estimation defined as distance from the boundary to the center. If observed ORR ranges from 20.0% to 34.3%, the precision estimation using 105 patients ranges from 7.7% to 9.1%.

Table 3: The 2-sided 95% Confidence Intervals for Observed ORR Based on a Sample Size of 105 Patients

Number of Responders	Observed ORR	95% CI	Precision
21	20.0%	(12.4, 27.7)	7.7%
24	22.9%	(14.8, 30.9)	8.0%
27	25.7%	(17.4, 34.1)	8.4%
31	29.5%	(20.8, 38.3)	8.8%
36	34.3%	(25.2, 43.4)	9.1%

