11.4.3.1. Primary Efficacy Analysis

Primary efficacy analysis will be performed when the last patient enrolled has had the opportunity for at least 4 tumor assessments.

The primary endpoint for efficacy analyses is the investigator-assessed ORR as determined by RECIST version 1.1 ([Eisenhauer, 2009](#)). The ORR is defined as the proportion of patients who achieve a best overall response (BOR) of CR or PR. Patients who are not evaluable for BOR will

be considered as non-responders. The ORR along with the 2-sided 95% confidence interval using a normal approximation of the binomial distribution will be summarized.

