1. OVERVIEW

The purpose of the statistical analysis plan (SAP) is to ensure the credibility of the study results by pre-specifying the statistical approaches for the analysis of study data prior to database lock. The SAP is intended to be a comprehensive and detailed description of the strategy and statistical methods to be used in the analysis of data for R2810-ONC-ISA-1981 study.

This plan may be revised during the study to accommodate protocol amendments and/or to make changes to adapt to unexpected issues in study execution and/or data that affect planned analyses. The final plan, if revised, will document all changes and be issued prior to database lock.

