2.2. Sample Size and Power Considerations

The planned total sample size for this study is 105 patients.

The primary objective of the study is to estimate the clinical benefit of cemiplimab + ISA101b after progression on first line chemotherapy, as assessed by objective response rate (ORR).

With 105 patients, [Table 1](#) below presents various response rates and associated 2-sided 95% CIs using a normal approximation of the binomial distribution, and precision of estimation defined as distance from the boundary to the center (i.e., half-width of the 95% CI). If observed ORR ranges from 20.0% to 34.3%, the precision estimation using 105 patients ranges from 7.7% to 9.1%.

Table 1: The 2-sided 95% Confidence Intervals for Observed ORR Based on a Sample Size of 105 Patients

Number of Responders	Observed ORR	95% CI	Precision
21	20.0%	(12.4, 27.7)	7.7%
24	22.9%	(14.8, 30.9)	8.0%
27	25.7%	(17.4, 34.1)	8.4%
31	29.5%	(20.8, 38.3)	8.8%
36	34.3%	(25.2, 43.4)	9.1%

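### Consider naming the Wilson method for the primary ORR interval: the planned interval is uncorrected Wald, which averages 94.3% coverage at n = 105 and tends to sit low; the effect is small and the plan is consistent

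*SAP*

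**What the plan says.** SAP 5.7.1 gives the ORR by investigator review and states that "the corresponding 2-sided 95% confidence interval will be derived using a normal approximation of the binomial distribution". Protocol 11.4.3.1 agrees ("The ORR along with the 2-sided 95% confidence interval using a normal approximation of the binomial distribution will be summarized"), and so does the synopsis. SAP 5.7.2 uses the same method for DCR and dDCR. SAP 5.7.3 lists subgroup analyses without naming an interval method.

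The sample size rests on the same interval. Protocol 11.2 tabulates "various response rates and associated 2-sided 95% CIs using a normal approximation of the binomial distribution". SAP 2.2 repeats the table, with "precision of estimation defined as distance from the boundary to the center (i.e., half-width of the 95% CI"), and concludes: "If observed ORR ranges from 20.0% to 34.3%, the precision estimation using 105 patients ranges from 7.7% to 9.1" percent.

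Protocol 11.1 states: "This is a single arm, open label study and there is no formal statistical hypothesis in this study". Protocol 6.2 and SAP 8 allow an administrative efficacy review once the first 53 patients have at least 4 tumour assessments each, and protocol 11.4.3 sets a data cutoff at that point to describe ORR.

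**The concern.** The term normal approximation does not identify one interval. Wald with or without continuity correction fits it, and the Wilson score interval is also built on a normal approximation. If the plain Wald form is meant, its coverage at this sample size is known to fall somewhat short of nominal, with unequal tails.

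This would hardly matter if a test carried the conclusion. Here there is no test, so the interval around the ORR is the whole primary inference, and its stated 95% should at least hold on average.

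**Working it through.** **Inputs.** n = 105 and two-sided 95% (z = 1.95996; SAP 2.2 and 5.7.1). The tabulated responder counts are 21, 24, 27, 31 and 36. The documents state no true ORR, so the tabulated observed rates, 20.0% to 34.3%, are taken as the range of true rates. This is an assumption. As a sensitivity check the range is extended down to the cemiplimab monotherapy figure in protocol 1.2 ("Patients on the cemiplimab arm had an ORR of 16.4% (95% CI 12.5% to 21.1" percent).

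**Step 1: which interval is it?** Wald is p ± z√(p(1−p)/n). For 21/105: 0.200 ± 1.96 × √(0.2 × 0.8/105) = 0.200 ± 0.0765, or 12.35% to 27.65%. The tables print 12.4 to 27.7. Over all five rows the tabulated limits agree with uncorrected Wald to about 0.05 point. Continuity-corrected Wald (add 0.5/n) gives 11.87 to 28.13 for 21/105. Across the table the largest discrepancies are 0.53 point for continuity-corrected Wald, 1.07 for Wilson and 1.23 for Clopper-Pearson. The plan therefore means uncorrected Wald, and its table is reproduced apart from rounding.

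**Step 2: the Wilson limits.** Centre = (p + z²/2n)/(1 + z²/n). Half-width = [z/(1 + z²/n)] × √(p(1−p)/n + z²/4n²). For 21/105, z²/n = 0.0366, the centre is 0.2183/1.0366 = 0.2106 and the half-width is 1.8908 × √(0.001524 + 0.000087) = 0.0759. The interval is 13.47% to 28.65%.

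| Responders | Wald | Half-width | Wilson (unrounded) | Half-width | Shift, lower / upper |
|---|---|---|---|---|---|
| 21 | 12.35, 27.65 | 7.65 | 13.470, 28.648 | 7.589 | +1.12 / +1.00 |
| 24 | 14.83, 30.89 | 8.03 | 15.868, 31.762 | 7.947 | +1.04 / +0.87 |
| 27 | 17.35, 34.07 | 8.36 | 18.316, 34.827 | 8.256 | +0.96 / +0.75 |
| 31 | 20.80, 38.25 | 8.72 | 21.647, 38.846 | 8.600 | +0.85 / +0.60 |
| 36 | 25.21, 43.36 | 9.08 | 25.906, 43.775 | 8.935 | +0.70 / +0.41 |

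**Step 3: exact coverage.** For each true rate π, coverage is the sum of the binomial(105, π) probabilities over those x from 0 to 105 whose interval contains π. This was evaluated in steps of 0.005 percentage point and averaged over the range.

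| Range of true ORR | Method | Mean | Minimum | Wholly below truth | Wholly above |
|---|---|---|---|---|---|
| 20.0–34.3% | Wald | 94.33% | 92.83% | 3.74% | 1.93% |
| 20.0–34.3% | Wilson | 95.04% | 93.61% | 2.21% | 2.76% |
| 20.0–34.3% | Clopper-Pearson | 96.14% | 95.01% | 1.90% | 1.97% |
| 16.4–34.3% | Wald | 94.26% | 92.18% | 3.89% | 1.86% |
| 16.4–34.3% | Wilson | 95.04% | 93.48% | 2.16% | 2.80% |

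Over 20.0–34.3%, Wald is below 95% at about 81% of rates and Wilson at about 45%. With the five tabulated rates taken in turn as the truth, Wald covers 93.57, 94.76, 93.75, 94.55 and 93.51%. Wilson covers 96.29, 95.28, 94.32, 95.86 and 94.98%.

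**Step 4: smaller samples.** At n = 53 over 20.0–34.3%, the Wald mean falls to 93.7% (minimum 91.2%), while Wilson still averages 95.0%. In a hypothetical subgroup of 10, Wald gives 0 to 0 for no responders and a lower limit of −8.6% for one. Wilson gives 0 to 27.8% and 1.8 to 40.4%.

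**The case against.** The strongest reply is that nothing here is wrong. The method is pre-specified identically throughout, the mean shortfall is 0.7 point (95.0 − 94.3), and the limits move by 0.4 to 1.1 points against half-widths of 7.7 to 9.1. Wald's misses lean low, which is the conservative direction for an activity estimate. All of this stands and limits the point to a suggestion.

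Wilson also meets the standard only in part. Its minimum is 93.6%, and at a true rate of 25.7% it covers 94.3%, the same as Wald's average. That stands too: Wilson restores 95% on average, not at every rate.

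The objection with most force concerns direction and timing. In an open-label, single-arm study with investigator-assessed response, changing the primary interval by SAP alone in a way that raises both limits could look data-driven. At 25/105, for example, the lower limit moves from 15.7% to 16.7%, across the 16.4% monotherapy ORR. The plan sets no comparison with that figure, so no conclusion turns on it, but it shows why the change must precede any look at efficacy.

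A reader might infer that the planned interval is invalid, that it exaggerates activity, or that the tables are miscalculated. The documents support none of these readings. The tables reproduce apart from rounding, the typical error understates ORR, and coverage stays above 92% in both ranges examined at n = 105.

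**Conclusion.** The point holds as a low-cost refinement. At n = 105 the planned uncorrected Wald interval covers about 94.3% on average over both 20.0–34.3% and 16.4–34.3%. It misses low about twice as often as high. Wilson averages 95.0% with marginally smaller half-widths and better balanced tails. The gain is larger at 53 patients.

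The result rests on assumed ranges of true ORR, since the documents give none. No claim is made outside those ranges, or that Wilson reaches 95% at each rate. With no hypothesis and no threshold, no decision in the plan would change.

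**What to change.** Make these SAP changes before any efficacy review, including the administrative review at 53 patients, and before database lock. SAP 1 provides the route: "The final plan, if revised, will document all changes and be issued prior to database lock".

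1. In SAP 5.7.1, in SAP 5.7.2 for DCR and dDCR, and in the SAP 2.2 lead-in, replace the normal-approximation wording with *the Wilson score method*.
2. In SAP 2.2, define precision only as the half-width of the 95% CI, because Wilson limits are not symmetric about the estimate (21/105: 6.5 points below, 8.6 above). Restate the precision range as 7.6% to 8.9%.
3. Replace the SAP Table 1 rows with: 21 (13.5, 28.6) 7.6; 24 (15.9, 31.8) 7.9; 27 (18.3, 34.8) 8.3; 31 (21.6, 38.8) 8.6; 36 (25.9, 43.8) 8.9.
4. Record in SAP 1.2.4 that the interval method departs from the protocol.
5. Use the same method for any ORR interval at the 53-patient review or in subgroups.

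If guaranteed coverage is preferred, name Clopper-Pearson alone and restate precision as about 8.1% to 9.4%.

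The cost is these edits and one option in the analysis program. The SAP will differ from protocol 11.2, 11.4.3.1 and the synopsis until the protocol is next amended, when those places should be brought into line.

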5.7.2. Analysis of Secondary Efficacy Variables

DOR: The distribution of DOR will be estimated using the Kaplan-Meier method. The median DOR along with its 95% CI will be presented and Kaplan-Meier estimates with 2-sided 95% CIs at specific time points will be summarized. DOR will also be summarized descriptively by range. Number and percentage of patients with DOR at specific time periods of interest will be summarized.

PFS: The distribution of PFS will be estimated using the Kaplan-Meier method. The median PFS along with its 95% CI will be presented and Kaplan-Meier estimates with 2-sided 95% CIs at specific time points will be summarized.

OS: The distribution of OS will be estimated using the Kaplan-Meier method. The median OS along with its 95% CI will be presented and Kaplan-Meier estimates with 2-sided 95% CIs at specific time points will be summarized. A variant of OS defined by censoring patients at the start date of subsequent therapy will be summarized and displayed by Kaplan-Meier approach as a sensitivity analysis.

TTR will be summarized descriptively and at specific time periods of interest.

DCR and dDCR will be summarized and the corresponding 2-sided 95% confidence intervals will be derived using a normal approximation of the binomial distribution.

The duration of response and the best percentage change from baseline in target lesions will be presented by swimmer plot and waterfall plot, respectively.

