3. HYPOTHESIS AND RATIONALE

3.1. Hypothesis

In recurrent/metastatic HPV16 cervical cancer patients who have progressed on or after first line chemotherapy in the recurrent or metastatic setting, cemiplimab + ISA101b will lead to durable objective responses in a clinically meaningful proportion of patients, and these will be associated with the production of increased anti-HPV16 E6/E7 effector T-cell responses.

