4.4.2. Secondary Efficacy Variables

Duration of response (DOR) is determined for patients with BOR of CR or PR. DOR is measured from the time measurement criteria are first met for CR/PR (whichever is first recorded) until the first date of recurrent or progressive disease (radiographic), or death due to any cause.

- Patients who do not have a documented tumor progression or death will be censored at the last evaluable tumor assessment.
- Patients who do not have a documented tumor progression or death before initiation of new anti-cancer therapy will be censored at the last evaluable tumor assessment prior to or on the date of new anti-cancer therapy.

Progression-free survival (PFS) is measured from the start of treatment until the first date of recurrent or progressive disease (radiographic), or death due to any cause.

- Patients who do not have a documented tumor progression or death will be censored at the last evaluable tumor assessment.

- Patients who do not have a documented tumor progression or death before initiation of new anti-cancer therapy will be censored at the last evaluable tumor assessment prior to or on the date of new anti-cancer therapy.
- Patients who do not have any evaluable post-baseline tumor assessment and do not die will be censored on the date of first study treatment.

Overall survival (OS) is measured from the start of treatment until death due to any cause. Patients who do not die will be censored at the last date that patient is documented to be alive. As many patients may receive new anti-cancer therapy after disease progression, a sensitivity analysis of OS will be conducted by censoring patients at the first date of a new anti-cancer therapy is taken.

Time to tumor response (TTR) is determined for patients with BOR of CR or PR. TTR is measured from the start of treatment until the time measurement criteria are first met for CR/PR (whichever is first recorded).

For all the above time-to-event variables, the time to event (day) is the date of event/censor - the date of first study treatment + 1.

Disease control rate (DCR) is determined by the portion of patients with BOR of CR, PR, or SD.

Durable disease control rate (dDCR) is defined as the proportion of patients best overall response of CR, PR, or SD without progression for at least 12 weeks.

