5. STATISTICAL METHODS

For continuous variables, descriptive statistics will include the following: the number of patients reflected in the calculation (n), mean, median, standard deviation, minimum, and maximum. In addition, 25th percentile and 75th percentile will be provided.

For categorical or ordinal data, frequencies and percentages will be displayed for each category. The denominator will be determined by the analysis population used for the summary.

For time-to-event variables, median time-to-event (and the survival rate at a fixed time point) and its two-sided 95% confidence intervals will be summarized by the Kaplan-Meier method, unless otherwise specified.

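### SAP 5.7.2 plans a crude percentage of patients with DOR at set times, with no denominator, time points or rule for earlier-censored responders; read over all responders, it understates durability at the primary cut-off, modestly at 3 months and severely at 12

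*SAP*

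**What the plan says.** SAP 5.7.2 plans several summaries of DOR. They include the Kaplan-Meier distribution, the median with its 95% CI, the range, and fixed-time estimates: "Kaplan-Meier estimates with 2-sided 95% CIs at specific time points will be summarized". It then adds: "Number and percentage of patients with DOR at specific time periods of interest". Protocol 11.4.3.2 plans only the Kaplan-Meier median and CI for DOR, so the count is a SAP addition.

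No sentence gives the denominator of that percentage. The relevant text is:

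- SAP 4.4.2: "Duration of response (DOR) is determined for patients with BOR of CR or PR".
- SAP 5, for categorical data: "The denominator will be determined by the analysis population used for the summary". SAP 5.7 makes the full analysis set (FAS) the population for efficacy.
- SAP 4.4.2, on responders without an event: "Patients who do not have a documented tumor progression or death will be censored at the last evaluable tumor assessment".
- SAP 6.4 leaves patients with missing data out of percentages, but does not say whether short follow-up is missing data.

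The timing is in SAP 5.7.1: "Primary efficacy analysis will be performed when the last patient enrolled has had the opportunity for at least 4 tumor assessments". Protocol 11.4.3 ties the final efficacy cut-off to the same event.

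**The concern.** A percentage of patients with DOR of at least t will be read as the chance that a response lasts that long. A responder who enrolled late and is still responding cannot reach the numerator if the last scan comes before t. Unless a rule removes that patient, the denominator keeps her, and censoring is scored in the same way as a response that ended. The figure then reflects the enrolment calendar as well as the treatment.

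Durability matters here. The hypothesis in Protocol 3.1 is that "cemiplimab + ISA101b will lead to durable objective responses in a clinically meaningful proportion of patients". The report could show two quite different percentages for what looks like the same quantity, and the SAP does not say which one measures durability. Because the time points and denominator are open, they could also be settled after the data have been seen.

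**Working it through.** **Plan's own figure.** The documents give no fixed-time DOR percentage. The only design figure is the ORR precision, which is not in dispute: 1.96 × √(p(1−p)/105) gives 7.65 to 9.08 points for 21 to 36 responders, against the stated 7.7 to 9.1.

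**Inputs from the documents.**
- Scans at weeks 7, 13, 19 and 25, then every 9 weeks (SAP 2.3). The fourth scan is at 7 + 6 + 6 + 6 = 25 weeks.
- Accrual of about 12 months (Protocol 6.1).
- Response confirmed at least 4 weeks later (SAP 4.4.1).
- Censoring at the last evaluable scan (SAP 4.4.2).

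**Assumptions not in the documents.** Uniform accrual; first response at weeks 7/13/19/25 in 60/25/10/5% of responders; exponential DOR with median 12 months (8 and 20 as a range); no dropout; time points of 3, 6 and 12 months.

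**Step 1: who can be observed for t months.** For a first response at week r, potential follow-up at the cut-off runs from L = (25 − r) × 12/52.18 months to L + 12. The share with at least t months is (L + 12 − t)/12, capped at 1.

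| First response | L (months) | t = 3 | t = 6 | t = 12 |
|---|---|---|---|---|
| Week 7 | 4.14 | 100% | 84% | 34% |
| Week 13 | 2.76 | 98% | 73% | 23% |
| Week 19 | 1.38 | 86% | 61% | 11% |

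For example, week 7 and t = 12 gives 4.14/12 = 0.345.

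**Step 2: simulation with confirmation, scan-dated progression and censoring at the last scan.** Accrual 12 months, median DOR 12 months, all responders as denominator:

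| t (months) | True | Kaplan-Meier | Crude | Crude/true |
|---|---|---|---|---|
| 3 | 93–94% | 93% | 87% | 0.93 |
| 6 | 84% | 83% | 62% | 0.74 |
| 12 | 59% | 57% | 13% | 0.22 |

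With 31 responders (a row of SAP Table 1), the crude count at 12 months would be about 31 × 0.131 = 4, while about 31 × 0.585 = 18 have responses that last that long. Over the FAS the same 4 patients would be 4/105, or about 4%.

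**Step 3: sensitivity of crude/true.** Ranges cover medians of 8, 12 and 20 months.

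| Accrual | t = 6 | t = 12 |
|---|---|---|
| 9 months | 0.65–0.66 | 0.05 |
| 12 months | 0.74 | 0.22–0.23 |
| 18 months | 0.83 | 0.48 |

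The ratio moves with accrual length and hardly at all with median DOR. Across all nine scenarios Kaplan-Meier is within 1 point of the truth at 6 months and about 1 to 4 points low at 12.

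**Step 4: a restricted denominator.** Keeping only responders whose first response is at least t before the cut-off gives 79% at 6 months and 47% at 12 in the Step 2 scenario. That is better than crude but still low: a patient can have t months to the cut-off and yet be censored before t at her last scan.

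**The case against.** The strongest reply is that a sound estimate is already planned. Kaplan-Meier estimates with CIs at fixed times stand in the same paragraph, and the count is a descriptive extra. An observed DOR of at least t is a true count; it misleads only when turned into a percentage and read as a probability. DOR is a secondary endpoint and Protocol 11.1 states no formal hypothesis, so no decision rule depends on it. This stands, and it keeps the point to one of reporting.

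Three stronger readings are tempting, and the documents do not support them.

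- A reader might infer that the SAP specifies all responders as the denominator. It does not. That is the natural reading of SAP 4.4.2, and the FAS is possible. The choice does not rescue the percentage, since the FAS makes it lower still. Nor would treating short follow-up as missing under SAP 6.4: early events in late-enrolled patients would stay in the denominator while their still-responding counterparts dropped out.
- A reader might infer that the percentage is far too low at any time point. The SAP names none. At 3 months the gap is about 6 to 7 points; it is severe only near 12.
- A reader might infer an unfair comparison with earlier studies. The documents give response rates, a median DOR and a DOR range for those studies, but no fixed-time DOR percentage to compare with.

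**Conclusion.** The point holds as a gap in specification with a predictable direction of bias. On either available denominator, a responder still responding but censored before t counts against durability. At the primary cut-off with about 12 months of accrual, the crude percentage over all responders is about three quarters of the true figure at 6 months and under a quarter at 12.

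The absolute percentages are illustrative, because they rest on uniform accrual, the assumed timing of responses and exponential DOR. The ratios are steadier across median DOR but depend on accrual: 0.65 to 0.83 at 6 months and 0.05 to 0.48 at 12 for accrual of 9 to 18 months. A later cut-off would shrink the shortfall.

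It should not be taken to mean that the plan lacks a valid durability estimate. The Kaplan-Meier estimate is there; what is missing is a statement that it is the durability measure.

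**What to change.** In SAP 5.7.2, name the time points and replace the sentence on the crude percentage with text to this effect: *The proportion of responders with DOR of at least t months is the Kaplan-Meier estimate with its 2-sided 95% CI. For each t, the observed number of responders with DOR of at least t is also given, labelled as observed, with the number who had an event before t and the number censored before t.*

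If a percentage restricted to responders whose first response is at least t before the cut-off is also shown, add a note that it remains biased low because censoring is at the last evaluable scan.

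While editing, reconcile the closing formula of SAP 4.4.2, which counts all the time-to-event variables from first study treatment, with the definition of DOR from first response. Applied literally, the formula would add the time to response to every DOR and push these counts up.

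The cost is a few SAP sentences and one table, with no change to conduct or data collection; SAP 1 already foresees revision before database lock. The downside is that no crude percentage appears at later time points.
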